11.3 Final Visit [Day 21 (± 2 Days)]

1. If applicable (female subject in reproductive age), pregnancy test
2. OSDI questionnaire application
3. Ocular symptomology enquiry
4. Complete ophthalmic exploration
5. Return of drug
6. Adverse events evaluation
8. Concomitant drug products assessment

11.4 Follow-up Phone Call [Day 36 (± 2)]

1. Investigate any adverse events related to the drug.

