9. STUDY SCHEDULE

Procedure	SCHEDULE (window periods)				
	Baseline visit	Visit 1	Visit 2	Final visit	Follow-up call
	Day 1	Day 7 (± 2)	Day 15 (± 2)	Day 21 (± 2)	Day 36 (± 2)
Eligibility criteria (inclusion and exclusion)	X				
Pregnancy test (if applicable)	X			X	
Informed consent signature	X				
General and ophthalmic medical record	X				
Ocular symptomatology (A, B, C)	X	X	X	X	
OSDI questionnaire	X	X	X	X	
Subject code assignment	X				
Visual capacity	X	X	X	X	
Previous biomicroscopy (D)	X	X	X	X	
Testing of epithelial defects with fluorescein dye	X	X	X	X	
Testing of epithelial defects with lissamine green dye	X	X	X	X	
Breakup time	X	X	X	X	
PIO measurement	X			X	
Posterior ophthalmoscopy under mydriasis	X			X	
Treatment delivery	X				
Start of drug application	X				
End of drug application				X ¹	
Drug return				X	
Subject diary submission	X				
Subject diary review		X	X	X	
Evaluation of adverse events		X	X	X	X
Evaluation of concomitant drug	X	X	X	X	
Follow-up call					X

9.1 Annotations to Activities Schedule:

- A. Burning
- B. Foreign body sensation
- C. Photophobia
- D. Includes testing of conjunctival hyperemia variable

¹ The application ends one day before to fulfill the 20 days indicated in the treatment.

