17. ADVERSE EVENTS

17.1 Adverse event, definition and communication

17.1.1 Overview

Adverse events (EA) may appear during the study, these may be associated or not with the study drug. If at any time any of the subjects may present any adverse event classified as serious that is derived from the drug's administration, the guidelines of the Official Mexican Norm 220 SSA1 2012 Installation and Operation of the Pharmacovigilance shall apply. The administration of the drug will be interrupted and the administration of an alternative therapy will be prescribed, as per the judgement of the main researcher.

An adverse event is any medical occurrence in a subject or subjects of a medical research, to whom a pharmaceutical product was administered and that does not necessarily have a causal relation with this treatment. Therefore. An EA can be any unfavorable and unintended sign (including an abnormal laboratory finding), symptom or disease temporally associated with the use of a medicinal (research) product, whether it is or not related to this.

The researcher must report the adverse events occurred during the study from the moment in which the subject signs the informed consent to be included in the clinical trial until the conclusion of the last procedure described in the approved version of the study protocol.

In all cases the etiology must be identified as far as possible and the sponsor must be notified. An “unexpected adverse event” is understood as any EA that is not identified in the nature, severity or frequency in the Researcher’s Manual or in the information of the risks described in this protocol.

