17.4 Characteristics of the report of serious adverse events

The researcher in charge and/ or person delegated for such task must report every adverse event, serious or non-serious that are presented during the development of the study, providing a diagnosis (name) to the condition(s) the subject presents.

It must be assured that the adverse events are correctly reported, grouping the signs and symptoms of the subject in clinical diagnosis.

In those cases in which the presence of several adverse events at once, and in which there is evidence that none of them correspond to the same pathological entity, each of the adverse events must be separately reported. For those surgical interventions programmed, the clinical diagnosis that caused the surgery must be reported instead of only the surgical event as such. For example: cholecystectomy (surgical event -NOT reported as adverse event); acute cholecystitis (Clinical diagnosis -reported as adverse event).

The reports of adverse events must indicate the date/ time of start, date/ time of conclusion, evolution and measures taken, as per the following:

- ❖ Solved
- ❖ Solved with aftereffects
- ❖ Being solved
- ❖ Unresolved
- ❖ Unknown

The information on the adverse events must be updated indicating the date of the kind of final solution of the adverse event or indicate as “being solved” for those cases in which the adverse event is still active.

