17.5.6 Reporte de los Eventos Adversos Serios

An active search of EAs must be performed using the spontaneous reports of the subject and physical explorations and interviews performed by the researcher during the visits.

If the EA ends up interrupting the study, the researcher must complete the FCR, in the section corresponding to Termination of the study, and specify if the event is serious or not.

A form of serious adverse events must be completed by the main researcher or the physician in charge and sent to the sponsor within the 24 hours following the notification; even if not all the required information is yet available at the moment. All the information gathered afterwards must be sent immediately once it is available. The researcher must provide an adequate and complete follow-up of the EAs. At any time they must provide an updated report of the EAs and report in writing when there is a final result for it.

In the same manner, all the EAs must be reported to the Committees of Ethics in Research, as well as the Regulatory authorities.

All the EAs as per the previous definitions and independently of the treatment or relationship with the study drug must be notified as soon as the event is known.

The researcher must notify the sponsor of the event sending the form "Serious Adverse Event Report" ("first notice") within the 24 hours after knowing about it via email with all the available information on the serious adverse event to the department of Pharmacovigilance of Laboratorios Sophia, S.A. de C.V as well as attaching a copy by email to the monitor in charge of the center.

17.5.7 Pharmacovigilance responsible:

[name] [name].

Email: [contact]

Laboratorios Sophia, S.A. de C.V.

[name]

[name]

[name]

[contact] (Direct)

[name]

[contact]

Direct assistance line, toll-free number: [name]

Non-serious adverse events (mild and moderate) are reported to the regulatory authority by the end of the study (after the report or in the report) and the serious adverse events immediately.

18. MONITORING AND AUDITING PROCEDURES.

Each research center as well as each researcher will have a clinical monitor assigned and authorized to revise, monitor and procure the information obtained from the study subjects.

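### Section 11.4 words the Day 36 call as a question about drug-related adverse events, which contradicts the unrestricted collection required by the schedule and sections 10.7, 17.1.1 and 17.4

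*Combined protocol and SAP*

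**What the plan says.** Section 11.4 lists a single item for the follow-up call on Day 36 (± 2): "Investigate any adverse events related to the drug". The corresponding items in section 11.2 (Visits 1 and 2) and section 11.3 (final visit) name an adverse-event evaluation with no such qualifier.

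The rest of the protocol sets no causality condition:

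- **Section 9 (schedule).** The row "Evaluation of adverse events" is marked at Visit 1, Visit 2, the final visit and the follow-up call.
- **Section 10.7.** The evaluation is to be done in accordance with section 17.
- **Section 17.1.1.** An adverse event is defined as one that "does not necessarily have a causal relation with this treatment". On the reporting period: "The researcher must report the adverse events occurred during the study from the moment in which the subject signs the informed consent", and this continues "until the conclusion of the last procedure described in the approved version of the study protocol".
- **Section 17.4.** The researcher "must report every adverse event, serious or non-serious that are presented during the development of the study".
- **Section 17.5.6.** Events "independently of the treatment or relationship with the study drug must be notified as soon as the event is known". The heading concerns serious events, although the sentence speaks of all of them.

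Section 17.5 has the main researcher assign causality to events that the subject has presented. Its categories include one for unrelated events and one for events that could not be assessed. Sections 6 and 13 list adverse events among the primary outcomes, and the table in section 13.3 measures them as a number of cases, not of related cases.

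**The concern.** The usual order, and the one in section 17, is to collect every event first and judge causality afterwards. Section 11.4 puts a causality condition into the question itself. Section 11 is the list that site staff work from at each contact, so the narrower wording may well be what is used on the telephone.

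The call is the only scheduled contact after the final visit. The schedule has no later examination, diary review or concomitant-drug check that would pick up an event the call did not ask about. If some sites follow 11.4 and others follow the schedule and section 17, a listed primary outcome has one definition up to the final visit and a site-dependent one afterwards.

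**Working it through.** The documents state no figure for this interval, so there is none to reproduce. The check sets the provisions side by side and then does the day arithmetic.

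**Is there a contradiction?**

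1. Under section 17.1.1 reporting ends with the last protocol procedure. In the schedule that is the Day 36 call, so the call lies inside the period in which events of any cause are reportable.
2. The schedule marks the unrestricted adverse-event row at the call, and section 10.7 ties that evaluation to section 17. Both point to collection regardless of cause.
3. Section 11.4 is the only provision that adds a relatedness condition, and it applies to the same call.
4. The qualifier is absent from sections 11.2 and 11.3, so it is not the section's standing shorthand for an adverse-event evaluation.

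The two instructions cannot both be followed as written.

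**How long is the interval?** Inputs are the final visit on Day 21 (± 2) and the call on Day 36 (± 2), both from section 9.

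- Nominal: 36 − 21 = 15 days (Days 22 to 36). As a share of Days 1 to 36: 15/36 = 41.7%.
- Shortest: final visit Day 23, call Day 34. 34 − 23 = 11 days; 11/34 = 32%.
- Longest: final visit Day 19, call Day 38. 38 − 19 = 19 days; 19/38 = 50%.

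These are shares of calendar time, not of events. At the nominal days the interval is off treatment. The schedule footnote says of the final visit: "The application ends one day before to fulfill the 20 days indicated in the treatment". Dosing therefore ends on Day 20, and the call falls 36 − 20 = 16 days after the last dose.

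**Which events are exposed?** Serious events, and events a subject volunteers, remain reportable under sections 17.4 and 17.5.6. What 11.4 leaves unasked is mainly the non-serious event that is thought unrelated and that the subject does not raise.

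**The case against.** The strongest reply is that 11.4 is one loosely worded line in a translated list, set against the schedule and sections 10.7, 17.1.1 and 17.4, all of which are unrestricted. A site that follows those collects everything. This stands as a limit on the consequence: the protocol does not say that only related events are collected, and the loss arises only where 11.4 is taken to govern. It does not remove the conflict, because nothing in the protocol says which provision prevails.

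Several stronger readings are tempting, and the documents do not support them:

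- **That the primary outcome is in fact filtered by causality for 15 of 36 days.** This assumes every site follows 11.4 over the other provisions.
- **That the comparison between arms is biased or unmasked.** Section 7.3 keeps the subject and treating physician blind, with identical bottles. A masked caller's view on relatedness has no access to the arm. Counts could be lowered, but no mechanism for an arm-dependent count is shown.
- **That delayed corneal events would be lost.** Section 4 names corneal abrasion and melting as adverse events of topical ocular anti-inflammatories of this class, and section 17.5.3 counts an event as possibly related when other causes cannot be ruled out. Such events are among the least likely to be screened out.
- **That a percentage of late events is missed.** If one assumes a share that would be judged unrelated, the loss equals that share, so the result only restates the assumption.
- **That relatedness would be judged outside the 17.5 categories.** Section 11.4 does not say who judges it or on what scale, and section 17.5 makes no exception for the call.

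The weight of the primary-outcome label is also limited. Section 12.4 sizes the trial on hyperemia and tear film breakup time only, section 13.2 places adverse events under safety, and section 14 gives no analysis specific to them. Nothing shows that Day 36 data enter a primary test, and no sample-size figure is affected.

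**Conclusion.** Wrong as written: an internal contradiction of minor severity. Section 11.4 is narrower than the schedule and sections 10.7, 17.1.1 and 17.4 for the same contact. Where a site follows 11.4, non-serious events thought unrelated would go unasked between the final visit and the call, nominally 15 days, or 11 to 19 with the windows. A listed primary outcome would then be under-ascertained and collected inconsistently across visits and sites.

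The conclusion rests on two readings: that the call is the last procedure in the sense of section 17.1.1, which the schedule supports, and that some sites would take 11.4 literally, which cannot be verified from the documents. The number of events lost cannot be computed, and a difference between arms is not shown.

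**What to change.** Reword section 11.4 so that the caller asks about any adverse event since the final visit, regardless of its relation to the drug, records it on the case report form, and has causality classified afterwards under section 17.5. That aligns 11.4 with the schedule and with sections 10.7, 17.1.1 and 17.4, so that the call's scope is the same wherever it is described.

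The cost is one sentence at a call that already takes place. It adds no visit or procedure and changes no dose, clinical rule or sample-size figure.

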12. POPULATION CHARACTERISTICS

- ❖ Adults ≥ 18 years and < 90 years.
- ❖ Both sexes.
- ❖ Clinical diagnosis of pterygium grade I to III (temporary and/or nasal).
- ❖ Enrollment duration of 6 months.

- ❖ Enrollment potential: once the research centers are opened, it is estimated that during the first month, inclusion will cover 30% of the size of the total sample.

12.1 Inclusion Criteria

- ❖ Age ≥18 and <90 years
- ❖ Both sexes
- ❖ Clinical diagnosis of pterygium grade I to III (temporal and/or nasal). According to the classification proposed by Johnston.⁹ (See attachment)
- ❖ Availability to attend check-ups when indicated.

12.2 Exclusion Criteria

12.2.1 General Criteria:

1. Subjects with topical or systemic medication that interferes significantly with the study results, such as topical immunomodulators, AINEs, antihistamines, corticosteroids, artificial tears with preservative, vasoconstrictors, etc. (see list of prohibited drug products).
2. Subjects (female) with an active sex life that do not use a hormonal contraceptive method, intrauterine device or bilateral tubal occlusion.
3. Female subjects that are pregnant or lactating.
4. Female subjects that tested positive in a urine base pregnancy test.
5. Positive for addiction* (verbal interview).
6. Subjects that have participated in any research clinical study in the last 40 days.
7. Legally or mentally incapacitated subjects unable to give their informed consent for their participation in this study.
8. Subjects that cannot keep appointments or follow through with all the protocol requirements.

*Definition: routine consumption of one or several psychoactive substances, till the point where the consumer (known as addict) periodically intoxicates themselves or does so in a constant manner,

shows a compulsive desire of using the preferred substance (or the substances), suffers an enormous difficulty to interrupt voluntarily or modify the consumption of the substance and seems determined to obtain it at any cost. –OMS definition*.

*** Addiction explanatory note: in the case of socially accepted drugs like tobacco and alcohol, their repetitive or continuous use is considered as addiction as well. In case of it being occasional (less than once per week) it must be completely suspended during a month prior to the study and during the study. In the case of ex-smokers (with more than one year without smoking) they shall not use substitutes like nicotine patches nor electronic cigarettes. In the case that there was another condition please consult the scientific committee of Laboratorios Sophia S.A. de C.V. to analyze each case in particular.*

12.2.2 Exclusion criteria related to ophthalmologic conditions:

Grade IV pterygium. According to the classification proposed by Jonhston9. (See addendum)

Dellen of the cornea.

Ocular surface neoplasia

Symblepharon.

Any type of corneal ulcers

Ocular surface disorders that result in scarring.

Metaplastic lesions in the ocular surface or adnexa.

History of autoimmune diseases that potentially can present ocular manifestations, like: rheumatoid arthritis, juvenile rheumatoid arthritis, Sjögren syndrome, seronegative spondyloarthropathies, Systemic lupus erythematosus, multiple sclerosis, arthritis of giant cells, Graves' disease, among others.

Infectious diseases

Ophthalmologic diseases that can potentially require treatment in the following 3 months.

Ocular surgical procedures (in the last 3 months)

Diseases in the previous segment that require treatment or endanger the visual prognosis (posterior uveitis, diabetic retinopathy, macular degeneration, etc.)

History of penetrating corneal transplantation.

History of scarring inflammatory diseases such as Steven-Johnson syndrome, pemphigus etc.

History of ocular allergic reaction and/or adnexa.

12.2.3 Elimination criteria of the subject included in the study:

1. Corneal damage clinically perceptible or evidenced in the staining of the surface (lissamine green and fluorescence) for example:

(a) Corneal de-epithelisation grade V (according to the Oxford scale)

(b) Corneal Melting.

(c) Corneal Dellen.

2. Added ocular surface diseases that require a treatment different to Zebesten ® or added treatments that are indicated for the new diagnostic.

3 Opacities in ocular transparent mediums (cornea, clear, vitreous body) that prevents the assessment of the anterior chamber or the following segment.

4. The subject's own decision.

5. Unable to keep the follow-up appointments.

6. Added not authorized treatment or self-medicated

7. Herbal treatments that affect the course of the disease or that produce other complications not related to the disease.

8. Systematic diseases that require immunomodulatory treatment or biologics that affect each line of the inflammatory cascade.

9. Retinal diseases secondary to chronic-degenerative diseases that require treatment to preserve the function and/or anatomy.

10. Inflammatory retinal diseases

11. Installation of uveitic picture in any ocular uveal level.

12. Uveitic picture that mean an ophthalmologic emergency that requires immediate treatment.

13. Ocular diseases that require surgical treatment.

14. Ocular diseases that require intravitreal injections.

12.3 PROHIBITED DRUG PRODUCTS

For purposes of this protocol, all drug products belonging to the groups listed in the 12.3.1 table are considered as prohibited, the drug product in the prototype column are examples of the most representative drug product of the group, however, they are not the only ones that are prohibited.

Table 12.3.1

Drug product group	Prototype	Route of administration	Resting period
Non-steroidal anti-inflammatory drugs	Ketorolac Diclofenac	Topical	8 weeks
Steroidal anti-inflammatory drugs	Dexamethasone, Prednisolone, Fluorometholone.	Topical and systematic	8 weeks
prostaglandin analogue	Latanoprost, Travaprost	Topical	12 weeks

Immune modulators	Ciclosporin	Topical	12 months
Vasoconstrictive	Naphazoline	Topical and systematic	2 weeks
Alpha 2 agonists	Brimonidine	Topical	4 weeks
Beta blockers	Timolol, betaxolol	Topical	4 weeks
Carbonic anhydrase:	Dorzolamide brinzolamide	Topical	4 weeks
Lubricants with conservatives	Hypromellose, Propylene glycol	Topical	2 weeks

12.4 SAMPLE SIZE CALCULATION

Sample size protocol SOPH155-0415/IV

According to the objectives of the study to evaluate the Zebesten ® effect in subjects with primary pterygium, the variables of primary outcome stipulated in the design were:

- Conjunctival hyperemia
- TRL

Both variables are considered, using similar literature, to perform the calculation of the sample size to meet with the study objectives.

Conjunctival hyperemia

The sample size was calculated according to the formula for the continuous quantitative variables:

$$n = 2 \frac{(Z_{\alpha/2} - Z_{\beta})(\delta)}{d^2}$$

With a statistical trust of 95% that corresponds to the type I error, and is the same as 1.96, with a potency of 80% that corresponds to the type II error, and equals to 0.84. It is considered as a standard deviation for the increase of 0.4 degrees of severity1 in the scale of conjunctival hyperemia after a pterygium surgery, with an expected difference of at least 2.9 degrees of severity.

Based on the previous the result was 69 cases (eyes) per group, which was incremented 20% by consideration of the losses (14 subjects), with **a total of 83 cases per group**, with a total population of study of **166 eyes to treat**.⁸

Tear film breakup time

The sample size was calculated according to the formula for continuous quantitative variables:

$$n = 2 \frac{(Z \propto -Z_1 - \beta)(\delta)}{d^2}$$

With a statistical trust of 95% that corresponds to the type I error, and is the same as 1.96, with a potency of 80% that corresponds to the type II error, and equals to 0.84. It's considered as a standard deviation for the increase of 1.47 seconds 2 in the tear film breakup time posterior to 60 days of ciclosporin application A, with an expected difference of at least 10.2 seconds.

Based on the previous the result was of 120 cases per group, which was incremented 20% per consideration to the losses (24 cases), with a total of **144 cases per group**, with a total population of study of **288 eyes to treat**.

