7.2 Sample

The total population will be 166 cases, which will be randomly included and distributed in 2 study groups. Both with diagnosis of grade I to III Pterygium.

Subjects with bilateral Pterygium, in which both eyes meet the selection criteria, can participate with both eyes, taking each eye as one case.

Group 1 will receive Zebesten® ophthalmic solution together with Na hyaluronate.

Group 2 will receive placebo (formulation with no drug substance) together with Na hyaluronate.

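### Section 12.4: the stated inputs do not give 69 or 120 eyes per group, so the 80% power behind 166 eyes is unsupported, and 166 is not reconciled with 288

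*Combined protocol and SAP*

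**What the plan says.** Section 12.4 names conjunctival hyperemia and tear film breakup time as the primary outcomes behind the sample size: "Both variables are considered, using similar literature, to perform the calculation of the sample size to meet with the study objectives". Both calculations use 1.96 for 95% confidence and 0.84 for 80% power.

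- **Hyperemia.** "It is considered as a standard deviation for the increase of 0.4 degrees of severity1", followed by "with an expected difference of at least 2.9 degrees of severity". Then: "Based on the previous the result was 69 cases (eyes) per group". A 20% allowance for losses raises this to 83 per group and 166 in total.
- **Breakup time.** The figure of 1.47 s is introduced in the same way as the 0.4, "with an expected difference of at least 10.2 seconds". Then: "Based on the previous the result was of 120 cases per group". The 20% allowance raises this to 144 per group, or "288 eyes to treat".

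Section 7.2 adopts the smaller total: "The total population will be 166 cases". Breakup time is a primary outcome in sections 6, 12.4 and 13, but is placed under safety in sections 5.1.2 and 13.2.

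**The concern.** Section 12.4 is where the protocol justifies enrolling 166 eyes. It gives every input to a textbook calculation, so the result should follow from them. As worded, the difference is about seven times the SD for each outcome (2.9/0.4 = 7.25; 10.2/1.47 = 6.94). With effects that large almost no eyes would be needed, yet the section reports 69 and 120 per group.

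If the result does not follow, a reader cannot tell what difference in hyperemia the trial was planned to detect or where the 80% comes from. The second gap is that one named primary outcome has its own derived total of 288, and the protocol enrols 166 without comment. It is then unclear whether the trial was meant to be sized for breakup time at all.

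**Working it through.** **Inputs (all from section 12.4).** z values 1.96 and 0.84, sum 2.80. Hyperemia: 0.4 and 2.9 grades. Breakup time: 1.47 and 10.2 s. Stated sizes before losses: 69 and 120 per group.

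**Loss step.** This reproduces as a multiplication by 1.2: 69 × 1.2 = 82.8, so 83; 120 × 1.2 = 144. The problem lies before this step.

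**Standard two-mean formula,** n per group = 2(z₁ + z₂)² SD²/d², where 2 × 2.80² = 15.68.

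| Reading | Hyperemia | Breakup time |
|---|---|---|
| 0.4 and 1.47 as SDs | 15.68 × 0.4²/2.9² = 0.30 | 15.68 × 1.47²/10.2² = 0.33 |
| 0.4 and 1.47 as differences | 15.68 × 2.9²/0.4² = 824 | 15.68 × 10.2²/1.47² = 755 |
| Stated in section 12.4 | 69 | 120 |

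**Formula as it appears in the text** (z values subtracted, nothing squared except d), with 0.4 and 1.47 as SDs: 2 × 1.12 × 0.4/2.9² = 0.107 and 2 × 1.12 × 1.47/10.2² = 0.032. Exponents may have been lost when the PDF was read, so these two figures carry no weight alone. The mismatch is there with or without the squares.

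**A near match for 120.** Exchange the inputs, subtract the z values (1.96 − 0.84 = 1.12) and keep the squares:

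- Breakup time: 2 × 1.12² × (10.2/1.47)² = 120.8.
- Hyperemia: 2 × 1.12² × (2.9/0.4)² = 131.9, not 69.

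The route comes close for breakup time but fails for hyperemia, the calculation that sets 166.

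**Power at the stated sizes under each reading.** With 0.4 and 1.47 as SDs, power is essentially 100% for both outcomes. With the inputs exchanged, it is 12.5% for hyperemia at 69 per group and 19.9% for breakup time at 120 per group. Neither reading gives 80%.

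**What can be said without the disputed inputs.** For two means and independent eyes at 80% power, the detectable effect is √(15.68/n) SD. At n = 69 this is 0.48 SD. If 20% of 83 are lost, 83 × 0.8 = 66.4 remain, and at n = 66 it is 0.49 SD.

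**166 against 288.** 288 − 166 = 122, and 166/288 = 58%. Neither section 7.2 nor section 12.4 gives a reason for the choice or the power left for breakup time.

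**The case against.** The text reads as a rough translation. The sentence that introduces 0.4 can be taken to mean that 0.4 is the increase, not the SD, so the result of 0.30 may rest on a reading nobody intended. That is fair, and both readings are shown above. The second gives 824 and 755, so it does not rescue the stated figures.

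One can also argue that the origin of the numbers is visible: inputs exchanged, z values subtracted. That gives 120.8 for breakup time, and with 1.65 in place of 1.96 it gives 2 × 0.81² × 7.25² = 69.0 for hyperemia. From there a reader might infer that the trial was really planned at about 12% to 20% power. The documents do not support that inference. Section 12.4 states 1.96, not 1.65. The route is a guess, and a printed input may itself be wrong.

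A reader might likewise infer that the trial is 122 eyes short for breakup time. But 288 does not follow from its own inputs either, so it cannot serve as a benchmark. Sections 5.1.2 and 13.2 also allow that breakup time was meant as a safety measure with hyperemia alone setting the size. If so, sections 6, 12.4 and 13 need correcting.

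Finally, a non-significant result is properly read from its confidence interval even when planning is sound. That stands. What is at stake is the stated justification for 166 eyes, not the ability to interpret the result.

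**Conclusion.** The point holds as an error in the stated justification. From the printed inputs the standard formula gives 0.30 or 824 eyes per group for hyperemia against the stated 69, and 0.33 or 755 for breakup time against 120. No reading worked through here with the stated z values gives 69. The 80% power attached to 69 evaluable eyes per group is therefore unsupported. It is not shown to be too low: depending on which figure is wrong, true power could lie on either side of 80%.

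Separately, the protocol says both outcomes are considered, derives 288 eyes for one of them and adopts 166 without explanation. That is a lack of reconciliation, not a demonstrated deficit.

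The calculations assume a two-sided comparison of two means with equal groups and independent eyes. Independence is doubtful because section 7.2 counts each eye of a bilateral subject as a case. A two-mean figure may also not suit hyperemia, which the section 13.3 table classes as ordinal and which section 14 would therefore present as frequencies and proportions.

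**What to change.** Rewrite section 12.4 and leave enrolment at 166 eyes.

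1. Print the formula with the z values added, and with the z sum and the SD squared.
2. For each outcome, first identify the source. The marker on the breakup-time input leads to a pterygium-excision outcomes study in section 21, and no title listed there concerns ciclosporin. For hyperemia, the marker on 0.4 leads to a bromfenac review, while the paragraph closes with a different reference. Then state which figure is the SD and which the difference, correct any wrong input, and recompute.
3. Replace the 80% claim with the power or detectable difference that 166 eyes give under the confirmed inputs and the test planned in section 14, allowing for hyperemia being ordinal. Until then, state only: *For a two-mean comparison of independent eyes, 69 evaluable eyes per group detect about 0.48 SD at 80% power (about 0.49 SD at 66 per group); if both eyes of a subject receive the same arm and their outcomes are positively correlated, the detectable difference is larger.* The condition is needed because section 7.5 randomises subjects while section 7.2 distributes cases.
4. State whether breakup time is a primary outcome that the trial is sized for. If it is, report its power at 166 eyes once its inputs are confirmed. If it is not, correct sections 6, 12.4 and 13.

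The cost is the redrafting and a search for the sources, with no change to enrolment, visits or data. The stated 80% power may have to be given up.
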